#### **7.2** Source Documents

In most cases, the source documents are contained in the participant's medical record and data collected on the CRFs must match the data in the medical records. In some cases, the CRF, or part of the CRF, may also serve as source documents. In these cases, a document should be available at the investigator's site and clearly identify those data that will be recorded in the CRF, and for which the CRF will stand as the source document. All original source documentation is expected to be stored at the site for the longest possible time required by applicable local regulations.

# 7.3 File Retention and Archiving

To enable evaluations and/or audits from regulatory authorities or the Sponsor, the investigator agrees to keep records, including the identity of all participating participants, all original signed ICFs, copies of all CRFs, SAE forms, source documents and adequate documentation of relevant correspondence (e.g., letters, meeting minutes, telephone calls reports).

Each site will receive a study site file at study initiation which contains all documents necessary for the study and is updated throughout the study. This file must be available for review in the event the site is selected for monitoring, audits, or inspections and must be safely archived for at least 15 years after the completing participation in the study unless local regulations require a longer archival period. No records can be destroyed during this time without agreement from the Sponsor and no records may be transferred without agreement from the Sponsor. Documents to be archived include the participant enrolment log and the signed ICF. If archiving of the file is no longer possible at the site, the site will be instructed to notify the Sponsor.

# 7.4 Quality Assurance and Monitoring

A study quality assurance and monitoring plan, which is proper for the study design, will be developed and implemented.

During the remote site initiation visit, the monitor will provide training on the conduct of the study to the investigator, co-investigator(s), and all site staff involved in the study. To ensure the integrity of the data, sites will be monitored. Remote site monitoring will be performed by IQVIA CRAs or Sponsor representatives to examine compliance with the protocol and

Template No.: RWI\_TP\_EPI0011 Revision 2 Reference: RWI\_WI\_EPI0005

ARMGO Pharma, Inc. RYR1-RM Study Version 4.0 dated 10-SEP -2024 Protocol/Study No.: CL-EPI-001

Page 48 of 64

adherence to the data collection procedures, to assess the accuracy and completeness of submitted clinical data and to verify that records and documents are being properly maintained for the duration of the study. The monitor will perform source data verification by reviewing the original participant records.

The monitor will close out each site remotely after the last participant's final follow-up assessment is completed, all data have been entered and all outstanding monitoring issues have been resolved or addressed. All monitoring procedures and the frequency of monitoring visits will be described in a monitoring plan. Monitor contact details for each participating site will be maintained in the Investigator Site File.

Representatives of the Sponsor's quality assurance unit/monitoring team and competent regulatory authorities must be permitted to inspect all study-related documents and other materials at the site, including the Investigator Site File, the completed eCRFs and the participants' original medical records. Audits may be conducted at any time during or after the study to ensure the validity and integrity of the study data.

#### 7.5 Data Management

A data management plan will be created before data collection begins and will describe all functions, processes, and specifications for data collection, cleaning, and validation. The eCRFs will include programmable edits to obtain immediate feedback if data are missing, out of range, illogical or potentially erroneous. A concurrent manual data review will be performed based on parameters dictated by the plan. Ad hoc queries will be generated within the EDC system and followed up for resolution.

High data quality standards will be kept, and processes and procedures will be used to repeatedly ensure that the data are as clean and correct as possible when presented for analysis. Data quality will be enhanced through a series of programmed data quality checks that automatically detect out of range or anomalous data.

# 7.6 Changes to the Protocol

Changes to the protocol will be documented in written protocol amendments. Major (i.e., substantial, significant) amendments will usually require submission to the relevant institutional review board (IRB)/independent ethics committee (IEC) for approval or favourable opinion. In such cases, the amendment will be implemented only after approval or favourable opinion has been obtained.

Minor (non-substantial) protocol amendments, including administrative changes, will be filed at each participating site, and will be submitted to the relevant IRB/IEC or regulatory authorities where required by pertinent regulations. Any amendment that could impact the participant's

Template No.: RWI\_TP\_EPI0011 Revision 2 Reference: RWI\_WI\_EPI0005

ARMGO Pharma, Inc. RYR1-RM Study Version 4.0 dated 10-SEP -2024 Protocol/Study No.: CL-EPI-001

Page 49 of 64

agreement to participate in the study requires their informed consent prior to continued participation.

# 7.7 Study Governance

Not applicable.

## 7.8 Publication Policy

Any publication of the results from this study must be consistent with the Sponsor's publication policy and guided by the Uniform Requirements for Manuscripts Submitted to Biomedical Journals: Writing and Editing for Biomedical Publication of the International Committee of Medical Journal Editors, updated April 2010. The rights of the investigator and of the Sponsor about publication of the results of this study are described in the applicable investigator contract with Sponsor.

All reporting will be consistent with the STROBE (Strengthening the Reporting of Observational studies in Epidemiology) Initiative checklist for cohort studies STROBE 2008.

#### 8. SAFETY REPORTING

All AEs, regardless of their relationship to use of the Syde® medical device or study procedures will be monitored and reported throughout the study. The AE reporting period begins when the participant is included into the study (date of first signature of informed consent) and continues till the end of study as defined by the Sponsor. AEs will be recorded on the appropriate forms (e.g., CRFs, eCRFs) as designated by the Sponsor.

# 8.1 Definitions

#### Adverse events

An AE is any untoward medical occurrence in a participant or clinical study subject that is administered a medical device or undergoing a study procedure and does not necessarily need to have a causal relationship. An AE can therefore be any unfavourable and unintended sign symptom, or disease temporally associated with the use of a device or study procedure, whether considered related to the medical device or study procedure or not.

If, according to the investigator, there is a worsening of a medical condition that was present prior to the exposure to a medical device or study procedure, this should also be considered a new AE and reported. Any medical condition present prior to the administration of the Syde® medical device or study procedure that remains unchanged or improved should not be recorded as an AE at subsequent visits.

Template No.: RWI\_TP\_EPI0011 Revision 2 Reference: RWI\_WI\_EPI0005

ARMGO Pharma, Inc. RYR1-RM Study Version 4.0 dated 10-SEP -2024 Protocol/Study No.: CL-EPI-001 Page 50 of 64

Documentation regarding the AE should be made as to the nature, date of onset, end date, severity, relationship to Syde® medical device or study procedure, action(s) taken, and outcome of any sign or symptom observed by the physician or reported by the participant upon indirect questioning.

#### Serious adverse events

An SAE is any experience that suggests a significant hazard, contraindication, side effect or precaution. An SAE must fulfil at least one of the following criteria:

- Results in death:
- Is life-threatening as it occurred (participant was at risk of death at the time of the event; this does not refer to an event which might have caused death if it were more severe);
- Requires inpatient hospitalization or prolongation of existing hospitalisation;
- Results in persistent or significant disability/incapacity (defined as a substantial disruption of a participant's ability to conduct normal life functions);
- Results in a congenital anomaly or birth defect; or
- Constitutes an important medical event (based upon appropriate medical judgment, event may jeopardize the participant and may require medical or surgical intervention to prevent one of the outcomes listed above).

#### Event severity

Event severity is defined as a qualitative assessment of the degree of intensity as determined by the investigator or reported to them by the participant. The assessment of severity is made irrespective relationship or seriousness of the event and should be evaluated according of the following scale:

- Mild: The event is noticeable to the participant, but is easily tolerated, and does not interfere with the participant's daily activities;
- Moderate: The event is bothersome, requiring additional therapy, and may interfere with the participant's daily activities;
- Severe: The event is intolerable, necessitates additional therapy or alteration of therapy, and interferes with the participant's daily activities.

**Note**: The terms "severe" and "serious" are not synonymous. Severity refers to the intensity of an AE (as in mild, moderate, or severe pain); the event itself may be of minor medical

Template No.: RWI\_TP\_EPI0011 Revision 2 Reference: RWI\_WI\_EPI0005

ARMGO Pharma, Inc. RYR1-RM Study Version 4.0 dated 10-SEP -2024 Protocol/Study No.: CL-EPI-001 Page 51 of 64

significance (such as severe headache). "Serious" is a regulatory definition and is based on participant or event outcome or action criteria usually associated with events that pose a threat to a participant's life or vital functions.

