# 8.2 Procedures for Reporting AEs in the Case Report Form

All AEs (serious and non-serious) reported during the study visits will be captured on the appropriate study CRF including the description, seriousness criteria, severity, duration (onset and resolution date), causal relationship with the Syde® medical device or study procedure, actions taken, and outcome.

The outcome of each AE (serious or non-serious) should be entered with a term such as those described below:

- recovered without sequelae
- recovered with sequelae
- ongoing
- change in severity grade (worsening, improving)
- died

Template No.: RWI\_TP\_EPI0011 Revision 2 Reference: RWI\_WI\_EPI0005

ARMGO Pharma, Inc. RYR1-RM Study Version 4.0 dated 10-SEP -2024 Protocol/Study No.: CL-EPI-001 Page 52 of 64

If any of the same AEs occur on several occasions in the same participant, then the AE in question must be documented and assessed each time.

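### Protocol 8.1 defines adverse event severity as intensity but ties Moderate and Severe to treatment need, so a bothersome or activity-limiting event that needs no therapy fits none of the three grades

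*Protocol*

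**What the plan says.** Protocol 8.1, under Event severity, opens with the concept: "Event severity is defined as a qualitative assessment of the degree of intensity as determined by the investigator". The note that closes the subsection repeats it: "Severity refers to the intensity of an AE (as in mild, moderate, or severe pain". Between the two stand the grades:

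- The lowest grade is silent on treatment and asks for good tolerance without interference: "Mild: The event is noticeable to the participant, but is easily tolerated, and does not interfere with the participant's daily activities".
- The middle grade brings in treatment need and leaves interference optional: "Moderate: The event is bothersome, requiring additional therapy, and may interfere with the participant's daily activities".
- The top grade demands all three components, and it alone accepts a change of existing treatment: "Severe: The event is intolerable, necessitates additional therapy or alteration of therapy, and interferes with the participant's daily activities".

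No fourth grade, fallback rule or alternative scale appears anywhere in the protocol.

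Severity is not optional. The Adverse events paragraph of 8.1 lists it among the items to document, and 8.2 states "All AEs (serious and non-serious) reported during the study visits will be captured on the appropriate study CRF including the description, seriousness criteria, severity". Section 8.2 also records actions taken as its own item and offers a change in severity grade, worsening or improving, as one of the outcome terms.

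**The concern.** The concept is intensity alone. The grades combine three things: how well the event is tolerated, whether it needs treatment, and whether it interferes with daily activities. Because the conditions within each grade are joined, an event can fail every grade on a component that has nothing to do with its intensity.

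Two kinds of event fall through. One interferes with daily activities but needs no therapy: the interference rules out Mild, and the absence of a need for therapy rules out Moderate and Severe. The other is bothersome without limiting activities and again needs no therapy. The note in 8.1 supplies an awkward case of its own: it gives a severe headache as an event that may be of minor medical significance, yet such a headache could not be graded Severe if it called for no therapy.

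What is at stake is consistent recording. Grades are assigned at the site when the event is entered, so a later analysis rule could not reliably restore them. There is also a knock-on for the outcome term in 8.2: a judgement that therapy is now needed could move an event into a different grade although its intensity has not changed.

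**Working it through.** The protocol gives no figure to reproduce. The check is to apply the three definitions as written to every kind of event they could meet.

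**Inputs (Protocol 8.1, Event severity)**

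- Tolerability: easily tolerated, bothersome, intolerable (3 levels).
- Therapy need: none, alteration only, additional (3 levels). Alteration is kept apart because only Severe mentions it.
- Interference with daily activities: no, yes (2 levels).

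This gives 3 × 3 × 2 = 18 profiles.

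**Conditions as written**

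- Mild: easily tolerated and no interference; silent on therapy. Covers 1 × 3 × 1 = 3 profiles.
- Moderate: bothersome and additional therapy; interference optional. Covers 1 × 1 × 2 = 2 profiles.
- Severe: intolerable, and additional or altered therapy, and interference. Covers 1 × 2 × 1 = 2 profiles.

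Graded: 3 + 2 + 2 = 7. Ungraded: 18 − 7 = 11.

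**The part that matters: events that need no therapy**

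| Tolerability | No interference | Interference |
|---|---|---|
| Easily tolerated | Mild | no grade |
| Bothersome | no grade | no grade |
| Intolerable | no grade | no grade |

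One of six has a grade, and none of the three that interfere with daily activities does. If Moderate is read generously so that altered therapy also counts, two more profiles gain a grade (9 of 18 ungraded), but this table does not change.

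**Is deleting the therapy clauses enough?** Without them, 3 × 2 = 6 profiles remain. Mild covers 1, Moderate 2 and Severe 1, so 6 − 4 = 2 stay ungraded: easily tolerated but interfering, and intolerable but not interfering. Moderate and Severe therefore also need alternative criteria (either tolerability or interference).

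**Does the alternative wording close the gap?** Take interference at three levels (none, some, prevents usual activities), giving 3 × 3 = 9 profiles. With Moderate as bothersome or some interference, and Severe as intolerable or prevents usual activities, all 9 receive a grade. Two satisfy both Moderate and Severe: bothersome and preventing activities, and intolerable with some interference. A rule that the highest grade met applies resolves both.

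**The case against.** The strongest reply is that the scale was never meant as a logical test. It is introduced as a qualitative judgement, and both the opening sentence and the note point the grader to intensity. An investigator following that concept would call a bothersome, limiting event Moderate and move on. This is fair as a forecast of practice: sites probably will choose a nearest grade, and few events will be left blank. It does not remove the defect. The text that tells the grader what Moderate means still contains a treatment condition, and two reasonable graders can resolve the conflict differently.

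It is also fair that the wording concerns need, not receipt. An event that required therapy but went untreated can still be graded.

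A reader might infer more than the protocol supports:

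- That limiting, untreated events are the expected after-effect of repeated maximal testing. The protocol prescribes maximal effort in 4.4.1.1 but gives no expected after-effects or rates; 4.1 provides rest between tests, and section 5 foresees no risk from the device.
- That 11 of 18 (61%) approximates the share of events left ungraded. It counts logical combinations, some of them implausible, and changes with the grid: treating therapy as yes or no gives 7 of 12. Neither is an event rate.
- That the battery's tolerability would be misjudged in a known direction. Nothing shows which grade sites would choose. If they did downgrade, the tests would look better tolerated than they were, not worse.
- That a main result is exposed. Tolerability is not an objective or endpoint in Table 1, 6.2.2.2 promises only a descriptive summary of adverse events, and neither the seriousness criteria in 8.1 nor authority reporting in 8.3 uses the grade.

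**Conclusion.** The point holds, as a minor one. The grades in 8.1 do not follow the definition of severity that surrounds them, and as written they leave no grade for an event that needs no therapy unless it is both easily tolerated and free of interference with daily activities. Since a severity is required for every adverse event, sites must improvise, and grading may be inconsistent between them.

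The size is limited. The effect stays within the descriptive adverse event summary of a study enrolling up to 20 participants. Description, duration, causality, actions taken and outcome are recorded separately, so no event is lost.

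The conclusion rests on reading each grade as a set of joined conditions, as its wording stands. How often an affected event would occur cannot be judged from the protocol.

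**What to change.** In 8.1, take the therapy clauses out of Moderate and Severe and grade on intensity and interference only, for example:

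- Mild: easily tolerated and no interference with daily activities.
- Moderate: bothersome, or some interference with daily activities.
- Severe: intolerable, or prevents usual daily activities.
- Add: assign the highest grade met.

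Keep treatment under actions taken in 8.2, where it is already collected, so no information is lost. This changes how events are recorded, not how they are managed.

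The cost is the rewording of the three bullets plus one sentence in 8.1, and the matching change to the eCRF completion guideline. No additional data are needed.

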#### Relationship to study procedure

For all events reported in participants exposed to the Syde® medical device or study procedure, the treating physician or other reporting health care provider will be asked to assess the relationship of the AE/SAEs to the Syde® medical device or study procedure using the following definitions:

- Probable: A causal relationship is clinically/biologically highly plausible, and there is a correlation between the onset of the AE/SAE and administration of the Syde® medical device or study procedure and resolution of the AE/SAE;
- Possible: A causal relationship is clinically/biologically plausible and there is a correlation between the onset of the AE/SAE and administration of the Syde® medical device or study procedure;
- Unlikely: A causal relationship is improbable, and another documented cause of the AE/SAE is most plausible;
- Unrelated: A causal relationship can be definitively excluded, and another documented cause of the AE/SAE is most plausible.

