#### 4.2.1 Inclusion Criteria

The following criteria must be met to be enrolled in the study:

Template No.: RWI\_TP\_EPI0011 Revision 2 Reference: RWI\_WI\_EPI0005

ARMGO Pharma, Inc. RYR1-RM Study Version 4.0 dated 10-SEP -2024 Protocol/Study No.: CL-EPI-001 Page 23 of 64

- Male and female patients (biological sex\*) aged 18 years or older at Screening;
- Confirmed genetic diagnosis of *RYR1*-RM with autosomal dominant mutation and supporting clinical phenotype with demonstrable proximal weakness on at least one of the baseline study assessments;
- Evidence of at least one demonstratable muscle/motor function deficit assessed through Manual Muscle Testing (MMT) and scored using the Medical Research Council (MRC) Scale for muscle strength (17) on physical examination (see MRC scale described in Table 5);
- Able to walk 10 meters, with or without assistance e.g., with a cane (assessed using the 10 Meter Walk Test);
- Willingness and ability to comply with scheduled visits and study procedures;
- Willingness to be fitted with the Syde® device at Screening Visit (for inclusion in the exploratory objective analysis only); and
- Able to provide written informed consent and understand the study procedures in the informed consent form (ICF).

\*Biological sex of male or female is required for study inclusion based on the available normative values for the tests conducted, but all gender identities are eligible for inclusion in the study.

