#### 5. DEVICES

The use of digital tools, such as wearable devices and other remote sensors, allows for the continuous, objective, and sensitive measurements of a participant's functional ability during daily life. Validated class I medical wearable devices have been used in clinical trials for assessing functional outcomes in daily life for participants with neuromuscular disorders (48) including clinical trials of participants with Duchenne Muscular Dystrophy and can be used in both ambulant and non-ambulant participants with movement disorders. (49)

Participants will be provided with a wearable device to collect daily physical activities. The purpose of the wearable device is to accurately measure the movement and activity levels of

Template No.: RWI\_TP\_EPI0011 Revision 2 Reference: RWI\_WI\_EPI0005

ARMGO Pharma, Inc. RYR1-RM Study Version 4.0 dated 10-SEP -2024 Protocol/Study No.: CL-EPI-001

Page 42 of 64

the participant during normal daily living, outside of investigational site visits. The Syde® device consists of 2 sensors (and a docking station). It is a Class I medical device manufactured by Sysnav. There are no foreseeable risks and minimal inconveniences to the participants who will wear it. Participants will wear one sensor on each ankle.

As the wearable device battery requires recharging daily after use, the sensors will not be worn at night. Site personnel, the participant, and parents/caregivers will be trained on the correct use of the device. The device will be fitted on the participant in the clinic prior to the Stair Climb Test, in order to ensure that it is working well, which can be assessed as participant climbs the stairs. The device would be removed when participants take part in activities which could damage the sensors or where the device could be in contact with water. Detailed user instructions are provided in the wearable device participant manual and quick start guide.

The wearable device will be worn on both ankles daily for 30 ( $\pm$ 3) days (to be taken off only at night before sleeping) from Screening Visit [Syde® device fitting] to Visit 1 [Syde® device removal]).

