# 6.2 Data Analyses

#### **6.2.1** General Considerations

All computations and generation of tables, listings, and data for figures will be performed using SAS® version 9.2 or higher (SAS Institute, Cary, NC, USA).

Prior to database lock, a detailed, finalized SAP will be completed and approved. The SAP will contain a more comprehensive description of the methodology for the statistical analyses than outlined in this protocol. The SAP will provide full details of the analyses, the data displays, and the algorithms to be used for data derivations.

Continuous variables will be described using descriptive statistics of central tendency (median and mean) and dispersion (standard deviation, interquartile range, maximum and minimum values). Categorical variables will be summarized as counts and proportions of the total study population. The 95% confidence interval will be presented for estimates of means and proportions. Descriptive statistics for both continuous and categorical variables will be based on participants with non-missing responses to the variable. Frequencies and percentages of missing values in each variable will be reported.

Whenever applicable, the endpoints will be summarized by each visit and across the overall study period (e.g., average endpoint across study visits). Furthermore, the absolute change in the endpoints between (i) Screening and each follow-up visit, and (ii) between each consecutive follow-up visit will be calculated and summarized with descriptive statistics.

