# 8.3 Procedures for Reporting Adverse Events (AEs) to Local and Regional Health Authorities

In addition to recording the event on the CRF, all SAEs and non-serious AEs considered related to the Syde® medical device or study procedure, reported during study visits may also need to be reported to local health authorities and regional bodies as per local guidelines. The participating physician is responsible for maintaining compliance with local guidelines as well as with any applicable site-specific requirements related to the reporting of SAEs or other safety information to the local IRB/IEC that approved the study.

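### Section 8 grades adverse-event causality against the Syde device and the study procedures jointly, so for related events arising between Screening and Visit 1 the grade does not show which was judged the cause

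*Protocol*

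**What the plan says.** **The causality question.** Protocol section 8.1, under Relationship to study procedure, says that the physician "will be asked to assess the relationship of the AE/SAEs to the Syde" "medical device or study procedure using the following definitions". The grades are Probable, Possible, Unlikely and Unrelated. The first two are defined by how the event's timing relates to the device or a study procedure, taken together.

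**The data recorded.** Section 8.2 lists the AE content of the case report form. It includes "seriousness criteria, severity, duration (onset and resolution date), causal relationship with the Syde" "medical device or study procedure, actions taken, and outcome". Section 8.3 sets its reporting trigger with the same joined wording, "non-serious AEs considered related to the Syde® medical device or study procedure", and the Safety paragraph of the synopsis matches.

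**The two exposures.** Section 4.5 and Table 9 schedule the strength, walking, sit-to-stand and stair tests at all four visits. Sections 4.4.3 and 5 limit the sensors to the period from Screening to Visit 1, 30 (±3) days. Section 4.2.1 requires willingness to wear them "for inclusion in the exploratory objective analysis only".

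**The concern.** The wearable and the test battery differ in who receives them, for how long, and in the harm one would look for. A single grade against either of them records that something in the study was suspected, without saying what.

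The protocol has a use for that distinction. Its exploratory objective is to evaluate the device for use in this population, and the whole study is meant to inform the choice of Phase II endpoints. Planners choosing between a wearable measure and a demanding clinic battery would want to know which one produced the related events.

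This is also a gap that later analysis cannot close. If the physician's attribution to one source is not asked for when the event is recorded, no statistical analysis plan can create it.

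**Working it through.** No power or sample-size formula applies, because the study is descriptive with up to 20 participants. The check compares the sections and measures how much follow-up lies in the ambiguous interval.

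**1. Is a separate rating requested anywhere?** I compared the AE documentation list and the rating question in 8.1, the form content in 8.2, the reporting trigger in 8.3 and the synopsis. All join the two exposures with *or*. None asks for a grade for each.

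**2. Which grades are ambiguous?** *Unrelated* and *Unlikely* reject both causes, so joining them loses little. *Possible* and *Probable* are met by either cause, so these two lose the attribution.

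**3. Which events are ambiguous?**
- Never fitted: only study procedures can be the cause. Separable.
- Fitted, onset after removal at Visit 1: the device is no longer worn, so the onset date separates these, assuming no delayed device effect.
- Fitted, onset from Screening to Visit 1: both exposures are in play. Not separable by date alone.

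Within the third group, Screening is the tightest case. Fitting and the first test battery share a calendar date, and 8.2 records dates, not times. Section 5 has the sensors fitted before the stair climb so that their function can be checked during it; a fall at that moment involves both. (Section 4.5.1, said to be in order of collection, lists fitting after the stair climb. The two sections need reconciling. Under 4.5.1 the exposures follow one another on the same day rather than coincide.) Removal and the second battery also share a visit.

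**4. How long is the interval?** Inputs are the windows in section 4.1: Visit 1 at 30 ±3 days, then two intervals of 30 days with −14/+3.
- Reproducing the protocol's follow-up range: minimum 27 + 16 + 16 = 59 days; maximum 33 + 33 + 33 = 99 days. Both match.
- Nominal wear share: 30/90 = 33%.
- Smallest share: 27/(27 + 33 + 33) = 27/93 = 29%.
- Largest share: 33/(33 + 16 + 16) = 33/65 = 51%.

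These shares are per wearer and refer to the visit period. AE collection runs from consent to the end of study, so the share of the full reporting period is smaller. Two of the four test sessions, Screening and Visit 1, fall at the ends of the wear interval.

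**The case against.** **The form is not shown and might hold two fields.** Section 8 defines a scale and lists content; it does not say there is exactly one field. This stands. If the form already has two, only the protocol wording needs to follow it.

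**Most events can be sorted anyway.** Description, onset and resolution dates and actions taken are recorded, and fitting and removal occur at known visits. Section 5 says the sensors are off during clinic visits, apart from the stair-climb check, so a fall at home in the third week did not happen during a test. With at most 20 participants, each related event can be read from a listing. This also stands, and it rules out the stronger reading that device and testing events cannot be separated at all. What remains is a small group, such as leg or ankle soreness soon after Screening, where the description may fit either cause.

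**Device fitting is itself listed as a study procedure in Table 9.** A joint rating is therefore coherent. It is, but section 8 names the device separately each time, so the authors did see two sources.

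A reader might infer more than the protocol supports on three further points:
- *Denominators.* Section 6.2.1 reports categorical variables as "counts and proportions of the total study population", and one might conclude that device-event rates lose their denominator. They do not: the number fitted is known from a scheduled procedure, the sentence is a general rule, and AE denominators are ordinarily set in the statistical analysis plan. Sections 4.5.1 and 5 also read as if everyone is fitted, against the optional wording in 4.2.1.
- *Section 8.3.* Relatedness to either source triggers it, so no event goes unreported because of the joint grade.
- *The safety statement in section 5.* It says "There are no foreseeable risks and minimal inconveniences to the participants who will wear it". Testing that is not a study objective; the exploratory endpoint is activity, such as stride velocity. Separate ratings in 20 participants would not settle it either.

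**Conclusion.** The point holds in a limited form. Section 8 asks for causality against two sources jointly. For related events with onset between Screening and Visit 1 in participants fitted with the device, the grade does not show which source the physician meant. That interval is about a third of nominal visit follow-up for a wearer. The number of events affected cannot be estimated, since the protocol gives neither an expected AE rate nor a number of wearers; with up to 20 participants it is likely to be small.

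The conclusion assumes that the form follows section 8 as written and that physicians give one grade to the joined exposure. It does not extend to events after removal, to participants never fitted, to denominators or to authority reporting. No primary or secondary strength, function or patient-reported endpoint depends on it. The priority is low to modest; the reason to act is that the change is cheap and the information cannot be derived afterwards.

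**What to change.** In sections 8.1 and 8.2, and on the AE form, require two ratings on the existing four-level scale:
- relationship to the Syde device, with *not applicable* for participants never fitted;
- relationship to study procedures, with the test named when the grade is Possible or Probable.

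State, in the protocol or the statistical analysis plan, that device-related events are summarised among participants fitted with the device. Section 8.3 can keep its trigger, read as relatedness on either rating. Reconcile sections 4.5.1 and 5 on whether the sensors are fitted before or after the Screening stair climb.

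The cost is one extra eCRF field per event and a few lines of wording, with no added visits or assessments. If the existing form already carries two fields, only the wording changes.
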